#### **4.3.1.2 Unsolicited AEs**

##### **4.3.1.2.1 Presence**

An observation will be considered an event if it has at least a verbatim term and is not a Grade 0 intensity event.

Grade 0 events should be included in separate listings.

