## 4 Endpoints and Assessment Methods

### 4.1 Safety Endpoints and Assessment Methods

The primary endpoints for the evaluation of safety are:

- Occurrence of any unsolicited systemic AEs reported in the 30 minutes after each and any injection of a SP0202 formulation or Prevnar 13, as applicable
- Occurrence of solicited (ie, pre-listed in the participant's DC / eDC and in the CRB) injection site reactions occurring up to D7 after each and any injection of a SP0202 formulation, Prevnar 13, or a concomitant pediatric vaccine, as applicable
- Occurrence of solicited systematic reactions occurring up to D7 after each and any injection of a SP0202 formulation or Prevnar 13, as applicable
- Occurrence of unsolicited (spontaneously reported) AEs up to 30 days after each and any injection of a SP0202 formulation or Prevnar 13, as applicable
- Occurrence of SAEs and AESIs, throughout the study period

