**Table 4.1: Solicited injection site reactions: terminology, definitions, and intensity scales**

CRB term (MedDRA lowest level term [LLT])	Injection site tenderness	Injection site erythema	Injection site swelling
Diary card term	Tenderness	Redness	Swelling
Definition	Pain when the injection site is touched or injected limb mobilized	Presence of a redness including the approximate point of needle entry	Swelling at or near the injection site Swelling or edema is caused by a fluid infiltration in tissue or cavity and, depending on the space available for the fluid to disperse, swelling may be either soft (typically) or firm (less typical) to touch and thus can be best described by looking at the size of the swelling
Intensity scale*	Grade 1: Minor reaction when injection site is touched  Grade 2: Cries or protests when injection site is touched  Grade 3 (CRB): Cries when injected limb is mobilized, or the movement of the injected limb is reduced  Grade 3 (DC / eDC): Cries when injected limb is moved or the movement of the injected limb is reduced	Grade 1: > 0 to < 25 mm Grade 2: $\geq$ 25 to < 50 mm Grade 3: $\geq$ 50 mm	Grade 1: > 0 to < 25 mm Grade 2: $\geq$ 25 to < 50 mm Grade 3: $\geq$ 50 mm

\* For the subjective reaction of tenderness, parents /guardians will record the intensity level (Grade 1, 2, or 3) in the diary card. For the measurable reactions of redness and swelling, they will record just the size of the reaction, and the classification as Grade 1, 2, or 3 will be assigned at the time of the statistical analysis.

Table 4.2: Solicited systemic reactions: terminology, definitions, and intensity scales

CRB term (MedDRA lowest level term [LLT])	Fever	Vomiting	Crying abnormal	Drowsiness	Appetite lost	Irritability
Diary card term	Temperature	Vomiting	Abnormal crying	Drowsiness	Loss of appetite	Irritability
Definition	Elevation of temperature to $\geq 38.0^{\circ}\text{C}$ ( $\geq 100.4^{\circ}\text{F}$ )	Vomiting does not include spitting up	Inconsolable crying without a determined reason	Reduced interest in surroundings, or increased sleeping	See intensity scale	An excessive response to stimuli: increased fussiness, whining, and fretfulness despite attempts to comfort the infant and despite caregiver responses that would normally be soothing

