##### **4.3.1.2.2 Intensity**

Intensity will be derived according to the following classification: None, Grade 1, Grade 2, Grade 3, or Missing.

If the unsolicited AE is measurable and its preferred term is part of the list of solicited reactions, then the measurement is derived based upon and following the same rule than the intensity scales defined in the protocol for that measurable injection site or systemic reaction.

Intensity for the other unsolicited AEs will correspond to the value reported in the CRF.

The maximum intensity corresponds to the highest intensity for a unique term.

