#### 4.3.1.2.6 SAEs

An event will be considered as a serious event if “Yes” is checked for “Serious” in the CRF.

SAEs will be analyzed throughout the study using at least the following periods:

- Within 30 days after (each) injection
- During post-Dose i period (ie, between injection i and injection i+1 [for each injection except for the last one of the primary series], and within 30 days after the last injection of the primary series for Infant)
- During the 6-month follow-up period (ie, from 31 days after the last injection until the last participant contact)
- During the study (ie, all SAEs occurred during the study)

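### Read literally, the Grade 0 rule could move a serious fever report with a recorded temperature below 38.0 °C out of the SAE tables, although the plan undertakes to count all SAEs

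*SAP*

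**What the plan says.** Four provisions of the SAP meet here.

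- **Presence of an unsolicited AE (4.3.1.2.1).** "An observation will be considered an event if it has at least a verbatim term and is not a Grade 0 intensity event". The next sentence deals with what is excluded: "Grade 0 events should be included in separate listings". Serious reports are not mentioned.
- **Intensity (4.3.1.2.2).** "Intensity will be derived according to the following classification: None, Grade 1, Grade 2, Grade 3, or Missing". For some terms the grade comes from a measurement: "If the unsolicited AE is measurable and its preferred term is part of the list of solicited reactions, then the measurement is derived" using the protocol's scale for that reaction. Other unsolicited AEs keep the intensity entered in the CRF.
- **SAEs (4.3.1.2.6).** The rule opens "An event will be considered as a serious event if" and then tests whether the Serious box is ticked. It sets no grade condition. One of its analysis periods covers every SAE during the study, and 5.1.1.2 likewise promises a table of all of them.
- **Primary safety endpoint (4.1).** "Occurrence of SAEs and AESIs, throughout the study period".

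A related rule is in 4.3.1.3.6. In the SOC/PT table, an unsolicited AE flagged as causing discontinuation counts only if its intensity is Grade 1 or higher, or missing. The disposition table instead counts any participant whose completion form gives an adverse event as the final status.

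**The concern.** Seriousness and intensity are separate attributes, and protocol 9.1.1.1 says so. A hospitalization makes an event serious whatever its grade. A filter based on a derived measurement is reasonable for trivial non-serious reports, but it should not decide whether a serious report enters a primary safety table.

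The rule also behaves oddly. A serious fever report with no recorded temperature has intensity Missing and is kept. The same report with 37.9 °C recorded has intensity None and, on the literal reading, is dropped, so the better documented case is the one that disappears from the summary.

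A programmer cannot apply the Presence rule to every unsolicited report and also tabulate every SAE. The SAP does not say which instruction prevails.

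**Working it through.** The plan gives no figure to reproduce. The check applies the rules in order and then sizes the effect of one report.

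**1. Does the measurement rule reach serious reports?** Yes. SAP 4.1.1.3 collects intensity for every unsolicited AE, serious or not, and uses the solicited scale for measurable terms. Protocol 9.1.1.1 includes SAEs among unsolicited AEs.

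**2. What is Grade 0?** The SAP does not define it. Of the five intensity categories in 4.3.1.2.2, None is the only one below Grade 1, so equating Grade 0 with None is an inference.

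**3. Apply the fever scale (SAP Table 4.2) to a report coded as fever and marked Serious.**

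| Recorded temperature | Derived intensity | Literal result |
|---|---|---|
| Not recorded | Missing | SAE table |
| 37.6 °C | None | separate listing only |
| 37.9 °C | None | separate listing only |
| 38.0 °C | Grade 1 | SAE table |
| 38.6 °C | Grade 2 | SAE table |
| 39.6 °C | Grade 3 | SAE table |

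**4. Which other terms could be affected?** Redness and swelling are also measurable, but SAP Table 4.1 makes any size above 0 mm and below 25 mm Grade 1. Only a recorded 0 mm could give None, which in practice leaves fever. The AESIs in SAP 4.1.1.4 (anaphylaxis, convulsions, hypotonic-hyporesponsive episode, apnea) are not measurable solicited terms. They keep their CRF intensity, on a scale that starts at Grade 1.

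**5. Size for one participant.** The inputs are the planned group sizes in SAP 5.5 (175 infants, 35 toddlers) and the SAP's Clopper-Pearson interval. For 0 of n the upper limit is 1 − 0.025^(1/n). For 1 of n the lower limit is 1 − 0.975^(1/n), and the upper limit is the 97.5% point of a Beta(2, n − 1) distribution.

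| Group size | Report left out | Report counted |
|---|---|---|
| 175 | 0/175 = 0% (0 to 2.09) | 1/175 = 0.57% (0.01 to 3.14) |
| 35 | 0/35 = 0% (0 to 10.00) | 1/35 = 2.86% (0.07 to 14.92) |

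The count of one is an assumption. Whatever the starting count, each participant lost shifts the percentage by 100/175 = 0.57 or 100/35 = 2.86 points. For example, 3/175 = 1.71% falls to 2/175 = 1.14%. A child who has another SAE in the same table would still be counted, so the overall participant percentage would not move.

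**The case against.** The strongest reply is that SAP 4.3.1.2.6 is the specific rule for SAEs and depends only on the Serious box. Where the authors want a grade filter they write one, as in 4.3.1.3.6. On that reading the commitment to all SAEs prevails and nothing is lost. This is a fair reading, and it is why the point is that a report could be left out, not that it will be. It does not remove the conflict: the SAE rule sits in the unsolicited AE section and begins from an event, a status that the Presence rule has just withheld from Grade 0 observations.

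The reply is also right about reach. Fever starting on days 0 to 7 is handled as a solicited reaction, so the unsolicited route mainly concerns onset from day 8. The report must also be coded as fever and not as an underlying diagnosis, and must carry a recorded value below 38.0 °C. For diary temperatures the site enters the highest reading (SAP 4.1.1.2).

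A reader might infer that SAEs will be lost from the trial, or that AESIs and injection-site reactions are exposed in the same way. The documents do not support either inference. Grade 0 records are listed. SAEs go to pharmacovigilance within 24 hours (protocol 10.1), and the two databases are reconciled before release for analysis (protocol 11.2). Steps 4 and 5 of the working show how little else the rule can touch.

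On discontinuations, the disposition and safety overview tables already count a participant through the completion form whatever the grade. Only the SOC/PT table can omit the event behind that status. AEs leading to discontinuation are not themselves a primary endpoint.

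**Conclusion.** The plan is wrong as written, through an internal conflict, and the consequence is minor. The Presence rule, taken literally, can exclude a serious fever report from tables that other sections and a primary endpoint say contain every SAE. The conclusion assumes that Grade 0 means None and that the Presence rule is applied before the SAE rule. Both assumptions are reasonable, but the SAP states neither.

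The documents give no expected frequency. They do not show that such a report will occur, and no hypothesis test is affected. The case for acting is that the tables are descriptive and the groups small, so a single omitted participant would be visible.

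**What to change.** In SAP 4.3.1.2.1, define the term and limit the exclusion, for example: *Grade 0 means a derived intensity of None. Observations marked Serious are events whatever the derived intensity; where that intensity is None, it is shown as None. The Grade 0 exclusion applies only to non-serious observations, subject to 4.3.1.3.6.* Showing None is preferable to recoding as missing, because the measurement was observed. No separate AESI exemption is needed.

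In 4.3.1.3.6, apply the same exemption to the grade filter: an unsolicited AE flagged as causing discontinuation enters the SOC/PT table whatever its derived intensity, within the stated period. The event table then agrees with the disposition table.

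The cost is a few sentences in the SAP. The Serious flag, discontinuation flag and measurements are already collected, so no new data are needed. SAE counts can only stay the same or rise slightly, and the filter keeps its purpose for other non-serious reports.

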##### **4.3.1.2.2 Intensity**

Intensity will be derived according to the following classification: None, Grade 1, Grade 2, Grade 3, or Missing.

If the unsolicited AE is measurable and its preferred term is part of the list of solicited reactions, then the measurement is derived based upon and following the same rule than the intensity scales defined in the protocol for that measurable injection site or systemic reaction.

Intensity for the other unsolicited AEs will correspond to the value reported in the CRF.

The maximum intensity corresponds to the highest intensity for a unique term.

#### 4.3.1.2.3 Last Vaccination

Last vaccination before an unsolicited AE is derived from the start date of the unsolicited AE provided in the unsolicited AE form and is calculated as follows:

- If an unsolicited AE has a complete start date and different to any of the vaccination dates, the start date should be used to determine the last vaccination before the unsolicited AE
- If the start date is missing or partially missing, or equal to any vaccination date, then the visit number in the “Appeared after Visit” or similar field, should be used to determine the last vaccination before the unsolicited AE

#### 4.3.1.2.4 Time of Onset

Time of onset is derived from the start date of the unsolicited AE and the date of last vaccination as described in Section [4.3.1.2.3](#).

Time of Onset = start date of the unsolicited AE - date of last vaccination before the unsolicitedAE

The time of onset should be considered as missing only if one or both of the dates are missing or partially missing.

The unsolicited AEs will be analyzed “Within 30 days” after each vaccination, which corresponds to AEs with a time of onset between 0 and 30 days or missing. An AE with missing time of onset will be considered to have occurred just after the vaccination indicated by the visit number in “Appeared after visit” or similar field, so will be included in these tables.

Time of onset period is displayed as D0-D3, D4-D7, D8-D14, D15 or later, and Missing.

Note: Unsolicited AE that occurred before vaccination (negative time of onset) or with a time of onset higher than defined above will not be included in analysis but will be listed separately.

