**4.1.1.3 Unsolicited Adverse Events**

In addition to recording solicited reactions, parents / guardians will be instructed to record any other medical events that may occur during the 30-day period after vaccination for toddlers / between the vaccination and the next visit for infants to be taken as per the study design. Space will be provided in the diary card for this purpose.

Information on SAEs will be collected and assessed throughout the study, from inclusion (D0) until 6 months after the last vaccination. Any SAE occurring at any time during the study will be reported by the Investigator in the CRB according to the completion instructions provided by the Sponsor; this includes checking the “Serious” box on the AE CRF and completing the appropriate Safety Complementary Information CRFs. All information concerning the SAE is to be reported either as part of the initial reporting or during follow-up reporting if relevant information became available later (eg, outcome, medical history, results of investigations, copy of hospitalization reports). In case a participant experiences febrile convulsion (neurological event associating fever and seizure), the assessment will be performed according to the “Guideline for definition and collection of cases of febrile convolution”, and this event will be considered an SAE.

For each unsolicited AE (whether serious or non-serious), the following information is to be recorded:

- Start and stop datesa
- Intensity of the event:

For measurable unsolicited AEs that are part of the list of solicited reactions, the size of the AE as well as the temperature for fever will be collected and analyzed based on the corresponding scale used for solicited reactions (see [Table 4.1](#) and [Table 4.2](#)).

All other unsolicited AEs will be classified according to the following intensity scale:

- Grade 1

CRB: A type of adverse event that is usually transient and may require only minimal treatment or therapeutic intervention. The event does not generally interfere with usual activities of daily living.

DC / eDC: No interference with usual activities.

---

a The stop date of all related AEs will be actively solicited. For other events, the investigator will provide the stop date when it becomes available. AEs for which no stop date was obtained during the course of the study will be considered as ongoing at the end of the study.

- Grade 2

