#### 5.3.1.4 Start Date and Stop Date

Missing or partially missing start dates or end dates for unsolicited AEs (including SAEs) will remain missing and not be imputed. If the start date is missing or partially missing, the time of onset will be considered to be missing. Nevertheless, unsolicited AEs with missing time of onset will be included in analyses according to the visit number collected in “Appeared after visit” or similar field. If either the start date or end date is missing or partially missing, the duration will be considered missing.

Missing or partially missing end dates for ongoing solicited AEs will remain missing and not be imputed.

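### A partly known AE start date is counted within 30 days of vaccination even when the known month proves onset after Day 30, so the 30-day unsolicited AE tables can include events from outside the window

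*SAP*

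**What the plan says.** Four provisions of the SAP act together.

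- **Onset (4.3.1.2.4).** Time of onset is the AE start date minus the date of the last vaccination. On incomplete dates: "The time of onset should be considered as missing only if one or both of the dates are missing or partially missing". A start date with known month and year but unknown day is handled like no date at all.
- **The 30-day window (4.3.1.2.4).** Unsolicited AEs are tabulated within 30 days, "which corresponds to AEs with a time of onset between 0 and 30 days or missing". On placement: "An AE with missing time of onset will be considered to have occurred just after the vaccination indicated by the visit number in" the field recording the visit after which the event appeared.
- **Choice of dose (4.3.1.2.3).** "If the start date is missing or partially missing, or equal to any vaccination date, then the visit number" in that field decides the dose. The known month is not consulted.
- **Missing data (5.3.1.4).** "Missing or partially missing start dates or end dates for unsolicited AEs (including SAEs) will remain missing and not be imputed", and "If the start date is missing or partially missing, the time of onset will be considered to be missing". Such events are then included by visit number.

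Late events are meant to leave the tables: an AE "with a time of onset higher than defined above will not be included in analysis but will be listed separately". That exclusion needs a computed time of onset, so it cannot act on a partial date.

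**The concern.** An inclusive convention is reasonable when the timing of an event is unknown. Here part of the timing is known, and the rule can assign a category that the known part contradicts. An AE with a complete date on Day 31 goes to a separate listing. The same AE recorded with its month only, where every day of that month falls after Day 30, is counted as within 30 days.

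Late events do reach the database. In SAP 4.1.1.3, parents record other medical events "between the vaccination and the next visit for infants", and infant visits after Doses 1 and 2 fall well beyond Day 30.

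Occurrence of unsolicited AEs up to 30 days after each injection is a primary safety endpoint (SAP 4.1). No hypotheses are tested, so the tabulated counts and percentages are themselves the result.

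**Working it through.** The documents give no count or rate of partial dates, so there is no figure of the plan's to reproduce. The check follows the rule through an example and then asks how often a known month could settle the matter.

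**Inputs from the documents**
- Dose 1 to Dose 2, and Dose 2 to Dose 3: 60 days, window ±14 (tables of study procedures for infants; Protocol 5.1.4). Range: 60 − 14 = 46 to 60 + 14 = 74 days.
- Window of interest: Day 0 to Day 30.
- Planned group size in Stage II: 175.

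**Criterion**
Earliest possible onset = first day of the known month − vaccination date. If this exceeds 30, every compatible date is after Day 30.

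**Examples**
- Dose 1 May 2021, AE start June 2021: possible onset Day 31 to Day 60. Under the SAP, onset is missing, so the AE is counted within 30 days.
- Dose 15 April 2021, AE start June 2021: possible onset Day 47 to Day 76, with the same result.
- Dose 15 April 2021, AE start May 2021: possible onset Day 16 to Day 46. The month does not settle it, and the inclusive rule is reasonable here.

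**How often the month settles it**
Assumptions: onset is uniform from the dose to the next visit, only the day is unknown, and dose dates are spread evenly over a year. All pairs of dose date and onset day were enumerated. Ranges show the effect of leaving out or including the day of the next visit. The third column leaves that day out and is (gap − 31)/gap.

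| Gap to next dose | Month alone proves onset after Day 30 | True onset after Day 30 |
|---|---|---|
| 46 days | 9% to 10% | 15/46 = 33% |
| 60 days | 24% to 25% | 29/60 = 48% |
| 74 days | 38% to 39% | 43/74 = 58% |

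These are shares of month-only dates, not of all AEs.

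**Size of one error**
One misplaced infant changes a group percentage by 1/175 = 0.57 percentage points.

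**The case against.** The strongest reply is that this is a disclosed, inclusive convention. It over-counts rather than hides events, it is the same in every group, and it feeds descriptive summaries only. Missing onset has its own row in the onset display, listings mark partial dates, sites must clarify incomplete diary entries, and SAEs are reported within 24 hours. All of that stands, and it makes few affected events likely. The row makes such events traceable but leaves them in the 30-day count, and none of these safeguards uses the known month. It is also fair that the study tables plan unsolicited AE collection for Day 0 to Day 30 only. Even so, infant diaries are kept to the next visit, and the SAP provides a listing for later onsets.

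Three stronger readings are tempting, and the documents do not support them.

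- **That the primary SAE endpoint is distorted.** The SAE and AESI endpoint is occurrence throughout the study (SAP 4.1), and moving an event between sub-periods cannot change it. Only the 30-day, post-dose and follow-up breakdowns in SAP 4.3.1.2.6 and 4.3.1.2.7 can shift. Those sections do not restate the missing-onset rule; it reaches them because SAEs are unsolicited AEs (Protocol 9.1.1.1) and SAP 5.3.1.4 names them.
- **That events first noted after V04, or at the 6-month call, are definitely placed within 30 days of the preceding dose.** V04 and V06 for infants, and V02 for toddlers, are not vaccination visits. The SAP does not say how such a visit number maps to a dose.
- **That about three quarters of month-only dates are provably late.** That share (about 75%) needs onset spread over 180 days after a dose. It does not describe the 46- to 74-day gaps, where the rule's effect is clear.

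**Conclusion.** The point holds as a limited misclassification. The SAP counts a partial-date AE within 30 days even when its known month and year exclude that, and no other provision corrects it. The 30-day unsolicited AE tables therefore can, rather than do, include events from outside the window, since at least one such date is needed.

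Under uniform onset with only the day unknown, the month proves late onset for about 9% to 39% of month-only dates after Doses 1 and 2. If onsets cluster soon after vaccination, the share is lower. The number of partial dates is not given and is probably small. SAE and AESI sub-period tables share the exposure; their whole-study counts do not. Toddler non-serious AEs are barely affected, because their recording stops at 30 days.

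The change is worth making because it is specific and nearly free, not because a large effect is expected.

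**What to change.** Add to SAP 4.3.1.2.4 and 5.3.1.4:

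*If the start date is partially missing, the known month and year are used. The event is counted within 30 days unless every date compatible with the known part is after Day 30 or before the vaccination. In that case it goes to the later period or to the separate listing.*

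Keep the current inclusive rule for fully missing dates and for partial dates compatible with Day 0 to Day 30. State that the same rule governs the SAE and AESI sub-periods.

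Do not treat an entry saying that the event appeared after V04 as proof of onset after Day 30. V04 may fall exactly on Day 30 (V03 + 30 days, window +14), and the blood-sampling text in Protocol 5.1.3 and SAP 3.2 prints ±14 days for that visit. Using V04 in this way could remove events that belong in the window.

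Cost: a short addition to the SAP, a few lines of code, and 30-day counts that may fall slightly. No event is lost, because those moved still appear in the later period or the listing.
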